8.4 Adverse Events of Special Interest

An AESI is an AE of scientific and medical interest specific to understanding of the IP and may require close monitoring and collection of additional information by the Investigator. An AESI may be serious or nonserious.

The rapid reporting of AESIs allows ongoing surveillance of these events in order to characterize and understand them in association with the use of this IP. All AESIs, regardless of seriousness or investigator-determined relationship to IP, must be reported to the Sponsor within 24 hours of site staff awareness by submitting an AESI Report Form by email to:

Email: [contact]

Alternatively, the AESI Report Form can be submitted by fax to:

US-Only [contact]

EX-US [contact]

The following AESIs will be particularly monitored in this study:

- Anaphylaxis and serious hypersensitivity reactions
- Infusion-related reactions
- Immune complex disease
- Cytopenia
- Serious and/or opportunistic infections, including PML (see Appendix A for list of opportunistic infections).

8.5 Other Events Requiring Immediate Reporting

8.5.1 Pregnancy

Pregnancy in a female subject who has received IP must be reported to the Sponsor (Section 8.3) within 24 hours of Investigator awareness of the event, by email or fax using the Pregnancy Report Form.

Subjects who become pregnant during the study period must not receive additional doses of IP but will not be withdrawn from the study. If the subject requests to know which treatment she received, this information will be provided to her. The pregnancy will be followed for outcome of the mother and child (including any premature terminations) and should be reported to the Sponsor's Patient Safety group after outcome.

Should the Investigator become aware of a pregnancy in the partner of a male study subject who has received IP, this should be reported to the Sponsor within 24 hours of knowledge of the event, by fax or email using the Pregnancy Report Form (see Section 8.3 for contact information). The Sponsor will endeavor to collect follow-up information on such pregnancies, provided the partner of the study subject provides consent.

8.5.2 Overdose or Misuse

Any instance of overdose of IP (suspected or confirmed) must be communicated to the Sponsor (Section 8.3) within 24 hours of Investigator awareness. Any associated AEs or SAEs must also be reported and their management should be recorded.

9 STATISTICAL CONSIDERATIONS

9.1 General Considerations

The analyses with a treatment policy strategy will include all data captured during the 52-week RCP, defined as the period from Day 1 (Dosing) at Visit 2 to the conclusion of the scheduled last RCP visit at Visit 15 (Week 52), inclusive.

The analyses applying the while-on-treatment strategy will include all data captured while subjects are on treatment, defined as the period from Day 1 (Dosing) at Visit 2 and 6 months after the last treatment during the RCP, inclusive.

Summary data will be presented in tabular format by treatment group. Categorical data will be summarized by the number and percentage of subjects in each category. Continuous variables will be summarized by descriptive statistics, including N, mean, standard deviation, median, and range. Data listings will be sorted by treatment group and patient number. Additional details of statistical analyses will be described in the statistical analysis plan (SAP).

9.2 Statistical Hypotheses

The following is the null and alternative hypotheses associated with the primary endpoint:

$$H_0: HR = 1 \text{ vs } H_1: HR \neq 1,$$

where *HR* indicates the hazard ratio of treated and AC-determined IgG4-RD flares relative to placebo. The hypothesized treatment effect of a relative reduction of 65% in risk implies a HR of 0.35.

different sample sizes between 160 and 200 in increments of 10. For each of the sample sizes, this simulation process will be repeated 10,000 times to give a distribution of the number of flares. The target sample size is the one that achieves 39 flares 90% of the time.

If the blinded assessment from these first 50 dosed subjects indicates that the number of flares expected with 160 subjects is less than 39, then the sample size may be adjusted based on the above exercise to the number of subjects anticipated to achieve 39 flares with a maximum of 200 subjects (100 subjects per treatment group).

9.4 Analysis Sets

Full Analysis Set: The Full Analysis Set will include all subjects randomized and who receive any dose of IP in the study. Subjects will be analyzed according to the treatment randomized. The efficacy analysis will be based on the Full Analysis Set.

Safety Analysis Set: The Safety Analysis Set will include all subjects who received any dose of IP during the RCP. Subjects will be analyzed according to the treatment that they actually received. Specifically, subjects randomized to inebilizumab who received all placebo doses will be included in the placebo group; conversely, subjects randomized to the placebo group who received at least one dose of inebilizumab will be included in the inebilizumab group. Safety, and ADA analyses will be based on Safety Analysis Set.

The Open-label Analysis Set: The Open-Label Analysis Set will include all subjects who receive any dose of inebilizumab during the OLP.

The Any Inebilizumab Analysis Set: The Any Inebilizumab Analysis Set will include all subjects who receive any dose of inebilizumab.

9.5 Methods for Statistical Analyses

9.5.1 Analysis of the Primary Efficacy Endpoint

The primary efficacy analysis will use the treatment policy strategy, which includes all data captured during the 52-week RCP.

The primary efficacy variable is the time in days from Day 1 (dosing) to the date of the first treated and AC-determined IgG4-RD flare within the 52-week RCP. The date of disease flare is defined as the date of initiation of any flare treatment (new or increased GC treatment, other immunotherapy, or interventional procedure) deemed necessary by the Investigator for the flare. The hazard rate in the inebilizumab group will be compared to that in the placebo group using the Cox proportional hazards model with the treatment indicator (inebilizumab or placebo) and the stratification factor as the explanatory variables. The HR of inebilizumab versus placebo will be estimated together with its associated 95% CI. SAS PROC PHREG will be used for fitting this model. The data cutoff for the primary analysis will be when all subjects have completed or discontinued from the RCP.

Subjects who discontinue prematurely from the RCP without a treated and AC-determined flare will be censored in this model at the time of discontinuation.

Additional analysis with the same model will be performed with data from subjects who meet the following criteria, censored at the time the relevant treatment was first received:

- Received any treatment for IgG4-RD, including GC or immunosuppressive treatment, prior to experiencing a treated and AC-determined flare; or
- Received any prohibited GC or immunosuppressive treatment prior to experiencing a treated and AC-determined flare.

9.5.2 Analysis of Secondary Efficacy Endpoints

9.5.2.1 Annualized Flare Rate for Treated and AC-determined Flares During the RCP

The annualized flare rate for treated and AC-determined flares during the RCP will be analyzed with a treatment policy strategy, which includes all data captured during the 52-week RCP. The efficacy variable is annualized flare rate, which will be compared between the inebilizumab group and the placebo group using a negative binomial model. The response variable in the model will be the number of treated AC-determined flares experienced by a subject over the 52-week RCP. The model will include covariates of treatment group (inebilizumab or placebo) and stratification factor. The logarithm of the subject's corresponding follow-up time will be used as an offset variable in the model to adjust for patients having different exposure times during which the events occur.

The estimated treatment effect (ie, the rate ratio of inebilizumab versus placebo), corresponding 95% CI, and two-sided p-value for the rate ratio will be presented. In addition, the annual flare rate and the corresponding 95% CI within each treatment group, and the absolute difference between treatment groups with the corresponding 95% CI, will be presented.

9.5.2.2 Annualized Flare Rate for AC-determined Flares During the RCP, Whether or Not Treated

The annualized flare rate for AC-determined flares, whether or not treated, during the RCP will be analyzed with a treatment policy strategy, which includes all data captured during the 52-week RCP. The efficacy variable is the annualized flare rate, which will be compared between the inebilizumab group and the placebo group using a negative binomial model. The response variable in the model will be the number of AC-determined flares, regardless of treatment experienced by a subject, over the 52-week RCP. The model will include covariates of treatment group (inebilizumab or placebo) and stratification factor. The logarithm of the subject's corresponding follow-up time will be used as an offset variable in the model to adjust for patients having different exposure times during which the events occur.

The estimated treatment effect (ie, the rate ratio of inebilizumab versus placebo), corresponding 95% CI, and two-sided p-value for the rate ratio will be presented. In addition, the annual flare rate and the corresponding 95% CI within each treatment group, and the absolute difference between treatment groups with the corresponding 95% CI, will be presented.

Clinical Study Protocol	Horizon Therapeutics Ireland DAC
VIB0551.P3.S2 - MITIGATE	Inebilizumab
Amendment 9.1, 08AUG2023	IgG4-Related Disease

9.5.2.3 Flare-free Treatment-free Complete Remission

Two types of flare-free complete remission will be analyzed: flare-free treatment-free complete remission and flare-free corticosteroid-free complete remission.

Flare-free treatment-free complete remission is defined as the lack of evident disease activity at Week 52, no AC-determined flare during the RCP, and no treatment for flare or disease control during the RCP except the required 8-week GC taper. Lack of evident disease activity is defined as either an IgG4-RD Responder Index (Wallace) score of 0, or a determination by the investigator that no disease activity is present based on physical, laboratory, pathology or other evidence.

Flare-free corticosteroid-free complete remission is defined as the lack of evident disease activity at Week 52, no AC-determined flare during the RCP, and no corticosteroid treatment for flare or disease control during the RCP except the required 8-week GC taper. Lack of evident disease activity is defined as either an IgG4-RD Responder Index (Wallace) score of 0, or a determination by the investigator that no disease activity is present based on physical, laboratory, pathology or other evidence.

The analysis of the proportion of subjects achieving each flare-free complete remission defined above for the composite estimand will include all data captured during the 52-week RCP. For both of these endpoints, the efficacy variable for each flare-free complete remission is the proportion of subjects achieving the corresponding flare-free complete remission at Week 52, which will be assessed using a logistic regression model respectively. The response variable in the model will be whether or not a subject achieves the corresponding flare-free complete remission at Week 52. The model will have treatment indicator (inebilizumab or placebo) and stratification factor as the explanatory variables.

Subjects who discontinue prematurely from the RCP will be treated as not achieving complete remission at Week 52. The results of the analyses will be presented using odds ratios, together with associated 95% CI and two-sided p-value for inebilizumab versus placebo.

An additional analysis under a treatment policy strategy with the same model will be conducted, with complete remission defined as the lack of evident disease activity at Week 52 and no AC-determined flare during the RCP.

9.5.2.4 Time to Initiation of Treatment for IgG4-RD, Regardless of AC Determination of Flare

The analysis of time to initiation of treatment for IgG4-RD activity by the Investigator within the RCP, regardless of AC determination of flare, will use a treatment policy strategy, which includes all data captured during the 52-week RCP. The date of disease flare is defined as the date of initiation of any flare treatment (new or increased GC treatment, other immunotherapy, or interventional procedure) deemed necessary by the Investigator for the flare.

The efficacy variable is the time in days from Day 1 (dosing) to the date of the first treatment for disease activity by the Investigator within the RCP, regardless of AC determination of flare within the 52-week RCP.

Clinical Study Protocol	Horizon Therapeutics Ireland DAC
VIB0551.P3.S2 - MITIGATE	Inebilizumab
Amendment 9.1, 08AUG2023	IgG4-Related Disease

The hazard rate in the inebilizumab group will be compared to that in the placebo group using the Cox proportional hazards model with the treatment indicator (inebilizumab or placebo) and the stratification factor as the explanatory variables. The HR of inebilizumab versus placebo will be estimated together with its associated 95% CI. SAS PROC PHREG will be used for fitting this model.

Subjects who discontinue prematurely from the RCP without receiving treatment for management of flare, as defined above, will be censored in this model at the time of discontinuation.

9.5.2.5 Glucocorticoid Use

The analysis of GC use will include all data captured during the 52-week RCP. For each subject, GC use will be calculated as the cumulative GC dose taken for the purpose of disease control during the RCP.

An analysis of covariance model with treatment indicator (inebilizumab or placebo) and stratification factor as the explanatory variables will be used.

GC use for a purpose other than controlling IgG4-RD will not be included in the analysis. For subjects who discontinue prematurely from the RCP, further GC use will be imputed as 0.

Results will be presented in terms of least square means (LSMEANS), treatment differences in LSMEANS, 95% CIs, and p-values.

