In an optional three-year OLP, all eligible subjects who choose to participate will receive inebilizumab (Section 7.4.2). Flare data collection will continue during this period, and the flare rate will be calculated. The OLP will also contribute to the safety database of inebilizumab in patients with IgG4-RD by increasing the number of patients exposed (those who originally received placebo and who then receive inebilizumab in the OLP) as well as the duration of exposure (in subjects who received inebilizumab in the RCP and then continue in the OLP).

In the OLP, subjects who were assigned to the placebo group during the preceding RCP will receive inebilizumab infusions on OLP Day 1 and Day 15, while those assigned to the inebilizumab group in the RCP will receive IV inebilizumab on OLP Day 1 and a matching placebo infusion on Day 15 to maintaining blinding of sites and subjects to the RCP treatment assignment. Both groups will then receive inebilizumab infusions every 6 months for the duration of the OLP.

Subjects who discontinue IP during the RCP will remain in the RCP for its duration and complete the Day 365 visit.

In addition, all subjects who discontinue IP during the OLP, or who do not participate in the OLP, will be asked to return to the clinic for a series of follow-up visits with limited assessments, occurring every six months for a total of two years after their last IP administration (see Section 6.4.1). This safety follow-up period (SFUP) will provide data on recovery of B cell counts and immunoglobulin levels and monitor for safety events after IP discontinuation.

An independent Safety Data Monitoring Committee (SDMC) charged with monitoring subject safety and ethical conduct of the study will periodically review study data and make recommendations regarding continued conduct of the study.

D = day; IV = intravenous.

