#### 3.5.2.6 Glucocorticoid Use

The estimand is defined by the following:

- Target population: Subjects in the FAS
- Variable: Cumulative GC dose taken for the purpose of disease control during the 52week RCP
- Intercurrent event: All data captured during the 52-week RCP will be used for analysis. GC use for a purpose other than controlling IgG4-RD or for protocol-specified steroid tapering will not be included in the analysis.
- Population-level summary: Difference in means GC dose between inebilizumab versus placebo and its associated 95% CI.

Total GC use per subject and daily GC use per subject will be summarized and analyzed by analysis of covariance models with treatment indicator (inebilizumab or placebo) and stratification factor as the explanatory variables. Results will be presented in terms of least square means (LSMEANS), treatment differences in LSMEANS, 95% Cis, and p-values.

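### Cumulative glucocorticoid use counts all time after withdrawal from the RCP as steroid-free, which biases the arm difference unless dropout times unobserved use is equal in the two arms

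*Protocol*

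**What the plan says.** Protocol 9.5.2.5 defines the variable: "GC use will be calculated as the cumulative GC dose taken for the purpose of disease control during the RCP". The model is given as: "An analysis of covariance model with treatment indicator (inebilizumab or placebo) and stratification factor as the explanatory variables will be used". For missing follow-up the rule is: "For subjects who discontinue prematurely from the RCP, further GC use will be imputed as 0".

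SAP 3.5.2.6 does not repeat the zero rule. It says "All data captured during the 52-week RCP will be used for analysis" and narrows what counts: "GC use for a purpose other than controlling IgG4-RD or for protocol-specified steroid tapering will not be included in the analysis". Its estimand variable is the cumulative dose and its summary is the difference in mean dose. It then adds a second measure: "Total GC use per subject and daily GC use per subject will be summarized and analyzed by analysis of covariance models". It does not define the denominator of daily use. It gives no rule for missing follow-up and no sensitivity analysis for this endpoint.

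The rule reaches only subjects who leave the RCP, because Protocol 4.1 keeps those who merely stop investigational product: "Subjects who discontinue IP during the RCP will remain in the RCP for its duration and complete the Day 365 visit".

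**The concern.** Zero is the lowest value that unobserved GC use can take, and it is assigned to people whose disease control is unknown. An arm's mean total is pulled down by the amount of follow-up it loses, multiplied by the GC use that would have occurred in that time.

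The plan handles the same problem differently elsewhere. The flare-rate analyses (Protocol 9.5.2.1 and 9.5.2.2, SAP 3.5.2.1 and 3.5.2.5) use log follow-up time as an offset. The remission analyses count leavers as failures: "Subjects who discontinue prematurely from the RCP will be treated as not achieving complete remission at Week 52". A sensitivity analysis of the primary endpoint (SAP 3.5.1.1) treats withdrawal for perceived lack of efficacy as a flare. The plan thus accepts that withdrawal can signal poor control, but GC use gets neither an adjustment nor a check.

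Limiting GC exposure is part of the stated rationale (Protocol Synopsis and 2.2), and this endpoint will be reported with confidence intervals and p-values.

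**Working it through.** **Equivalence of the two texts.** A subject's observed total plus zero for the missing time equals the sum of captured doses. The SAP's total-dose analysis therefore has the same property as the protocol's rule.

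**Inputs from the documents.** Protocol 9.3 assumes a placebo flare probability of 0.35 and a hazard ratio of 0.35. The hazards are −ln(0.65) = 0.4308 for placebo and 0.35 × 0.4308 = 0.1508 for inebilizumab.

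The plan gives no sizing for GC use, so the trial sizing is the only stated figure that can be reproduced:
- Events: 4 × (1.960 + 1.282)² / (ln 0.35)² = 38.1, rounded up to 39.
- Pr(Fail) = 0.245, and 39 / 0.245 = 159.2, rounded up to 160. Both agree with the plan.

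**Assumptions.** The documents give no RCP dropout rate for this trial and no mean GC dose per flare. I assume:
- flares recur at the planning hazards, with the same mean dose X per flare in both arms;
- dropout is exponential and independent of flares, with proportion d leaving within the year.

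**Formulas.** Write the difference as placebo minus inebilizumab, so a positive value means steroid sparing.
- Mean follow-up in years: m = d / (−ln(1 − d)).
- Observed mean total per arm: hazard × m × X.
- True difference: (0.4308 − 0.1508)X = 0.2800X.
- Shortfall: d_P·u_P − d_I·u_I, where u is mean unobserved GC use per discontinuer. Here d·u = hazard × (1 − m) × X.

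**Results.**

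| Dropout placebo / inebilizumab | m placebo / inebilizumab | Observed difference | Error relative to 0.2800X |
|---|---|---|---|
| 3% / 3% | 0.9849 / 0.9849 | 0.2758X | 1.5% too small |
| 10% / 10% | 0.9491 / 0.9491 | 0.2658X | 5.1% too small |
| 20% / 5% | 0.8963 / 0.9748 | 0.3861X − 0.1470X = 0.2391X | 14.6% too small |
| 5% / 15% | 0.9748 / 0.9230 | 0.2808X | 0.3% too large |
| 5% / 20% | 0.9748 / 0.8963 | 0.2848X | 1.7% too large |

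X cancels from the percentages. In milligrams, for X = 500, 1,000 and 2,240:
- the true difference is 140, 280 and 627 mg;
- the shortfall at 10% / 10% is 7, 14 and 32 mg;
- the shortfall at 20% / 5% is 20, 41 and 92 mg.

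The top value, 2,240, is 40 mg/day × 56 days, taken from the limits in Protocol 7.6 only to bound the range.

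**No drug effect.** With hazard 0.4308 in both arms and 5% placebo / 20% inebilizumab dropout, a false steroid-sparing effect of 0.4308 × (0.9748 − 0.8963)X = 0.034X appears. That is 7.9% of the mean annual use.

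**Follow-up-adjusted dose.** Total dose divided by total follow-up is (hazard × m × X) / m = hazard × X in each arm. Under non-informative dropout it returns 0.2800X in every row.

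**Informative withdrawal.** Suppose GC use after dropout runs at three times the arm's rate, with 20% / 5% dropout. The true difference becomes 0.4308 × (0.8963 + 3 × 0.1037)X − 0.1508 × (0.9748 + 3 × 0.0252)X = 0.3618X. The cumulative total gives 0.2391X (34% too small). The follow-up-adjusted dose gives 0.2800X (23% too small).

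**The case against.** The strongest case against pressing this is that little rides on it. GC use is the last of six secondary efficacy endpoints and lies outside Type I error control. The error-controlled steroid-sparing endpoint is corticosteroid-free remission, where leavers count as failures. Subjects who stop product stay in follow-up. The earlier NMOSD study had 97.0% RCP completion, though over 28 weeks. With 80 per arm and a fixed dose per flare, the standard error of the difference is about √((0.4308 + 0.1508)/80)·X = 0.085X, so the shortfalls at 10% / 10% and 20% / 5% are about 0.2 and 0.5 standard errors. The SAP also adds daily use, a Kaplan-Meier curve of RCP discontinuation, and by-subject corticosteroid listings. All of this stands, and it limits the priority of the point. It does not supply a missing-data rule or a denominator.

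Four stronger readings are tempting and are not supported:
- **Withdrawal is scored as the best outcome.** Only further use is set to zero. A subject treated for a flare who then leaves keeps that dose.
- **Bias appears whenever dropout differs, and favours the arm that loses more.** It appears at 10% / 10% and almost vanishes at 5% / 15%. What matters is dropout times unobserved use.
- **The SAP leaves the main version open.** It names cumulative dose as the estimand variable. What it leaves open is how daily use is defined and what role it plays.
- **Annualising the dose cures the problem.** It does so only when dropout is non-informative, as the last calculation shows.

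**Conclusion.** The point holds at moderate weight. Protocol 9.5.2.5, and SAP 3.5.2.6 by arithmetic, treat unobserved RCP time as free of GC. Under the planning hazards and non-informative exponential dropout, the steroid-sparing difference is about 1.5%, 5% and 15% too small at 3% / 3%, 10% / 10% and 20% / 5% placebo / inebilizumab dropout. These percentages assume equal mean dose per flare in both arms and do not depend on its value; the dropout rates are my assumptions.

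Under the planned effect, the material errors run against inebilizumab. If the drug had no effect and inebilizumab lost more subjects, the error would run in its favour. Withdrawal linked to poor control can make the error larger. The primary and key secondary analyses are untouched.

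**What to change.** 1. Delete the zero imputation from Protocol 9.5.2.5 and reconcile that section with SAP 3.5.2.6.
2. In the SAP, define daily GC use as disease-control dose divided by RCP follow-up time, and analyse it weighted by follow-up time. Alternatively, model dose with a log follow-up offset, as for the flare rates. Name this as the main estimate and align the estimand variable with it.
3. Keep the unadjusted cumulative total as a supportive analysis.
4. Add one sensitivity analysis for informative withdrawal, for example reference-based multiple imputation of GC use after discontinuation.

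The cost is wording in both documents and a little more analysis; daily use is already planned. The main downside is a change of scale from total to annualised dose for a non-key secondary endpoint, so it should be settled before unblinding.
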